## 6.5 POOLING OF CENTRES

This section is not applicable, because the study was performed in only one centre.

## 6.6 HANDLING OF MISSING DATA AND OUTLIERS

Data of screened subjects who were withdrawn from the trial prior to administration of any study drug will not be reported in the CTR.

Data of treated subjects who failed to complete the study (dropouts or withdrawals) will be reported in the CTR as far as their data are available. All withdrawals will be documented and the reason for withdrawal recorded in the CTR.

**CTP Section 7.4.1:** *With respect to safety evaluations, it is not planned to impute missing values.*

The only exception where imputation might be necessary for safety evaluation are AE dates. Missing or incomplete AE dates are imputed according to BI standards ([4](#)) [001-MCG-156\_RD-01].

Missing data and outliers of PK data are handled according to BI standards ([5](#)) [001-MCS-36-472\_RD-01]. **CTP Section 7.4.2: Drug concentration data identified with NOS (no sample available), NOR (no valid result), NOA (not analysed), BLQ (below the lower limit of quantification), or NOP (no peak detectable) will be displayed as such and not replaced by zero at any time point (this rule also applies also to the lag phase, including the predose values).**

**CTP Section 7.4.3: For the non-compartmental analysis, concentration data identified with NOS, NOR or NOA will generally not be considered. Concentration values in the lag phase identified as BLQ or NOP will be set to zero. All other BLQ/NOP values of the profile will be ignored. The lag phase is defined as the period between time zero and the first time point with a concentration above the quantification limit.**

## **6.7 BASELINE, TIME WINDOWS AND CALCULATED VISITS**

The last non-missing value determined prior to the study drug administration will be defined as baseline.

Time windows are defined in Section 6.1 of the CTP. Adherence to time windows will be checked at the RPM.

## 7. PLANNED ANALYSIS

The format of the listings and tables will follow the BI guideline "Reporting of clinical trials and project summaries" (6).

The individual values of all subjects will be listed, sorted by treatment group, subject number and visit. AE listings will be sorted by assigned treatment (see [Section 7.8.1](#) below for details). The listings will be contained in Appendix 16.2 (SDL) of the CTR.

The following standard descriptive statistical parameters will be displayed in summary tables of continuous variables:

N	number of non-missing observations
Mean	arithmetic mean
SD	standard deviation
Min	minimum
Median	median
Max	maximum

For plasma concentrations as well as for all PK parameters, the following descriptive statistics will additionally be calculated:

CV	arithmetic coefficient of variation
gMean	geometric mean
gCV	geometric coefficient of variation

For PK parameters the following descriptive statistics will additionally be calculated:

P10	10 th percentile
Q1	1 st quartile
Q3	3 rd quartile
P90	90 th percentile

The data format for descriptive statistics of concentrations will be identical with the data format of the respective concentrations. The descriptive statistics of PK parameters will be calculated using the individual values with the number of decimal places as provided by the evaluation program. Then the individual values as well as the descriptive statistics will be reported with three significant digits in the CTR.

Tabulations of frequencies for categorical data will include all possible categories and will display the number of observations in a category as well as the percentage (%) relative to the respective treatment group. Percentages will be rounded to one decimal place. The category missing will be displayed if and only if there are actually missing values. Percentages will be based on all subjects in the respective subject set whether they have non-missing values or not.

### 7.1 DEMOGRAPHIC AND OTHER BASELINE CHARACTERISTICS

Only descriptive statistics are planned for this section of the report. These will be based on the TS.

## 7.2 CONCOMITANT DISEASES AND MEDICATION

Concomitant diseases will be coded according to the most recent version of MedDRA. Concomitant medication will be coded according to the most recent version of the World Health Organisation – Drug Dictionary.

Only descriptive statistics are planned for this section of the report.

A medication will be considered concomitant to a dose group, if it

- is ongoing at the time of administration of this treatment, or
- starts within the analysis phase of the respective treatment (see [Section 6.1](#) for a definition of treatments and analysis phases).

The relevance of the concomitant therapies to the evaluation of PK will be decided no later than at the RPM.

## 7.3 TREATMENT COMPLIANCE

Treatment compliance will not be analysed as a specific endpoint (cf. [Section 5.4.2](#)). Any deviations from complete intake will be addressed in the RPM (cf. [Section 6.2](#)) and described in the CTR.

## 7.4 PRIMARY ENDPOINT

Analysis of relative bioavailability of the primary endpoints will be performed as defined in Sections 7.1.3 and 7.3.1 of the CTP.

The statistical model for the primary analysis defined in the CTP Section 7.1.3 is an analysis of variance (ANOVA) model on the logarithmic scale. For each matched pair a pair number will be assigned and included in the model as random effect.

The following comparisons will be analysed: T1/R, T2/R and T3/R.

**CTP Section 7.3.1:** *Further comparisons may be investigated if appropriate (e.g. T1 vs. T2 [...] ).*

A sensitivity analysis will be performed with matched pair as fixed effect.

Primary PK endpoints will also be assessed descriptively. The analysis of standard PK parameters is performed according to BI standards ([5](#)) [001-MCS-36-472\_RD-01].

### Exclusion of PK parameters

The ADS ADPP contains column variables APEXC and APEXCO indicating inclusion/exclusion (APEXC) of a PK parameter and an analysis flag comment (APEXCO). All analyses based on the PKS are based on PK parameter values which are not flagged for exclusion, i.e. with APEXC equal to 'Included'.

### Exclusion of plasma concentrations

The ADS ADPC (PK concentrations per time-point or per time-interval) contains column variables ACEXC or ACEXCO indicating inclusion/exclusion (ACEXC) of a concentration and an analysis flag comment (ACEXCO). Exclusion of a concentration depends on the analysis flag comment ACEXCO. For example, if ACEXCO is set to 'ALL CALC', the value will be excluded for all types of analyses based on concentrations. If ACEXCO is set to 'DESC STATS' the value will be excluded from descriptive evaluations per planned time point/time interval. If ACEXCO contains the addition 'TIME VIOLATION' or 'TIME DEVIATION', the value can be used for further analyses based on actual times. If ACEXCO is set to 'HALF LIFE', the value will be excluded from half-life calculation only; the value is included for all other analyses. Excluded concentration itself will be listed in the CTR associated with an appropriate flag.

Further details are given in "Noncompartmental Pharmacokinetic / Pharmacodynamic Analyses of Clinical Studies" (5) and "Description of Analytical Transfer Files and PK/PD Data Files" (7).

## **7.5 SECONDARY ENDPOINTS**

### **7.5.1 Key secondary endpoint**

This section is not applicable as no key secondary endpoint has been specified in the CTP.

### **7.5.2 Secondary endpoints**

The secondary PK endpoint will be analysed in the same way as the primary endpoints. A sensitivity analysis will also be performed with matched pair as fixed effect.

The endpoint will also be assessed descriptively. The analysis of standard PK parameters is performed according to BI standards (5) [001-MCS-36-472\_RD-01].

See [Section 7.4](#) of this TSAP for details regarding exclusion of PK parameters and plasma concentrations.

## **7.6 FURTHER ENDPOINTS**

### **7.6.1 Safety parameters**

Safety parameters will be analysed as described in Section 7.8 of this TSAP.

## **7.7 EXTENT OF EXPOSURE**

Treatment exposure will only be listed by subject and date and time of drug administration.

## 7.8 SAFETY ANALYSIS

All safety analyses will be performed on the TS.

### 7.8.1 Adverse events

AEs will be coded with the most recent version of MedDRA.

The analyses of AEs will be descriptive in nature. All analyses of AEs will be based on the number of subjects with AEs and not on the number of AEs.

For analysis, multiple AE occurrence data on the electronic case report form (eCRF) will be collapsed into one AE event provided that all of the following applies:

- All AE attributes are identical (LLT, intensity, action taken, therapy required, seriousness, reason for seriousness, relationship, outcome, AESI)
- The occurrences were time-overlapping or time-adjacent (time-adjacency of two occurrences is given if the second occurrence started at most 1 hour after the first occurrence ended).

For further details on summarization of AE data, please refer to "Analysis and presentation of adverse event data from Clinical Trials" (8) and "Handling of missing and incomplete AE dates" (4).

The analysis of AEs will be based on the concept of treatment emergent AEs. That means that all AEs will be assigned to the screening, treatment or follow-up phases as defined in [Section 6.1](#). AEs will be analysed based on actual treatments, as defined in [Table 6.1: 2](#).

An overall summary of AEs will be presented. This overall summary will comprise summary statistics for the class of other significant AEs according to ICH E3 (9) and for the class of AESIs.

**CTP Section 5.2.2.1: The AESI in this trial is hepatic injury, as defined by the following alterations of hepatic laboratory parameters:**

- *an elevation of AST (aspartate transaminase) and/or ALT (alanine transaminase)  $\geq 3$ -fold ULN combined with an elevation of total bilirubin  $\geq 2$ -fold ULN measured in the same blood sample, or*
- *aminotransferase (ALT, and/or AST) elevations  $\geq 10$  fold ULN*

The investigator had to classify on the eCRF whether an observed AE was an AESI or not.

According to ICH E3 (9), AEs classified as 'other significant' need to be reported and will include those non-serious and non-significant AEs

- (i) which are marked haematological or other lab abnormalities, or
- (ii) which were reported with 'action taken = discontinuation' or 'action taken = reduced', or
- (iii) which lead to significant concomitant therapy as identified by the Clinical Monitor/Investigator at a Medical Quality Review Meeting.

The frequency of subjects with AEs will be summarised by treatment, primary system organ class and preferred term. AEs which were considered by the investigator to be drug related

will be summarised separately. Separate tables will also be provided for subjects with SAEs, subjects with AESIs and subjects with other significant AEs (according to ICH E3 [\(9\)](#)). AEs will also be summarized by maximum intensity.

The system organ classes will be sorted by total frequency, preferred terms will be sorted by total frequency (within system organ class).

For disclosure of AE data on ClinicalTrials.gov, the frequency of subjects with non-serious AEs occurring with an incidence of greater than 5 % (in preferred terms) will be summarised by treatment, primary system organ class and preferred term. The frequency of subjects with SAEs will also be summarised.

For disclosure of AE data in the EudraCT register, the frequency of AEs, the frequency of non-serious AEs with an incidence of greater than 5 % (in preferred terms) and the frequency of SAEs will be summarised.

For support of lay summaries, the frequency of subjects with drug-related SAEs will be summarised by treatment, primary system organ class and preferred term.

### **7.8.2      Laboratory data**

The analyses of laboratory data will be descriptive in nature and will be based on BI standard "Display and Analysis of Laboratory Data" [\(10\)](#).

Analyses will be based on normalised values, which means transforming to a standard unit and a standard reference range.

Descriptive statistics of laboratory values over time and for the difference from baseline (see [Section 6.7](#)) will be provided. Frequency tables of changes between baseline and last value on treatment with respect to the reference range will be presented.

Possibly clinically significant abnormal laboratory values are only those identified either in the Investigator's comments on the eCRF or at the RPM at the latest. It is the Investigator's responsibility to decide whether a lab value is clinically significant abnormal or not. Standard or project-specific rules for flagging clinically significant values will not be applied in this study.

Clinically relevant findings in laboratory data will be reported as baseline conditions (at screening) or as AEs (during the trial) and will be analysed as such.

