Based on studies in healthy subjects, no specific drug-related risks are anticipated. Nevertheless, the following safety measures are/will be applied in this study in order to minimize the risk for the healthy subjects:

Proprietary confidential information © 2019 Boehringer Ingelheim International GmbH or one or more of its affiliated companies

- The study will start with Dose Group 1 and 2 (perumbilical SC dose of of BI 655130). Provided no dose limiting AEs occurred as approved by the Principal Investigator (or an authorised deputy) and the trial clinical monitor (or an authorised deputy) after in-depth analysis of all available safety data up to Day 10 (see [Section 3.1](#)), the study will pursue with Dose Group 3 (perumbilical SC dose of of BI 655130) and Dose Group 4 (SC dose of of BI 655130 in the thigh). Dose Group 3 will be divided into 2 cohorts. In the first week, 6 subjects will be treated. There will be an interval of at least 1 week after start of dosing in the first cohort before start of dosing of the second cohort of Dose Group 3.
- At any time during the ongoing study, further dosing will be stopped in case of safety and tolerability concerns based on the criteria defined in [Section 3.1](#).
- Monitoring of ECG, vital signs, and extensive safety laboratory testing ([Table 5.2.3:1](#)) is conducted throughout the study.
- After dosing, the subjects will stay at the site for at least 48 hours.
- BI 655130 will be administered in a hospital setting and subjects will be under close medical observation during their hospitalisation (see [Section 6.2](#)), as well as after their discharge and until the end of observation period. Safety will be closely monitored during site visits for both expected and unexpected adverse events.

Currently there are no data available to suggest interactions of BI 655130 [[c03320877-04](#)].

Although rare, a potential for drug-induced liver injury (DILI) is under constant surveillance by sponsors and regulators. Therefore, this study requires timely detection, evaluation, and follow-up of laboratory alterations in selected liver laboratory parameters to ensure subjects' safety, see also [Section 5.2.2.1](#), adverse events of special interest.

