6.2.2 Treatment period

Study participants will be admitted to the trial site in the evening of Day -1 and kept under close medical surveillance for at least 48 h following drug administration. The subjects will

Proprietary confidential information © 2019 Boehringer Ingelheim International GmbH or one or more of its affiliated companies

then be allowed to leave the trial site after formal assessment and confirmation of their fitness. On all other study days, the study will be performed in an ambulatory fashion.

Details on treatments and procedures of administration are described in [Section 4.1.4](#).

For details on time points and procedures for collection of plasma samples for PK analysis, refer to [Flow Chart](#) and [Section 5.5.2](#).

The safety measurements performed during the treatment period are specified in [Section 5.2](#) of this protocol and in the [Flow Chart](#). For details on time points for all other trial procedures, refer to the [Flow Chart](#). AEs and concomitant therapy will be assessed continuously from screening until the end of trial examination.

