Laboratory data will be compared to their reference ranges. Values outside the reference range as well as values defined as clinically relevant will be highlighted in the listings. Additionally, differences from baseline will be evaluated.

Vital signs or other safety-relevant data observed at screening, baseline, during the course of the trial and at the end-of-trial evaluation will be assessed with regard to possible changes compared to findings before start of treatment.

Relevant ECG findings will be reported as AEs.

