## 6. GENERAL ANALYSIS DEFINITIONS

### 6.1 TREATMENTS

For basic study information on treatments to be administered, assignments of dose groups, and selection of doses, cf. Section 4 of the CTP.

All subjects were planned to be treated with a single dose of BI 655130 injected subcutaneously in the abdominal region or into the thigh. See Table 6.1: 1 for details on the treatment schedule.

Table 6.1: 1 Dosage and treatment schedule

Dose Group	Total dose	Concentration of solution	Application volume	Injection site
1 (reference treatment R)				Perumbilical
2 (test treatment T1)				Perumbilical (left and right)
3 (test treatment T3)				Perumbilical (left and right)
4 (test treatment T2)				Thigh

The analysis phases specified in [Table 6.1: 2](#) will be defined for each subject for use in the statistical analysis of AEs, safety laboratory data, local tolerability and vital signs.

Table 6.1: 2 Flow chart of analysis phases for statistical analyses of AEs, safety laboratory data, local tolerability and vital signs

Study analysis phase	Label	Start (inclusive)	End (exclusive)
Screening	Screening	Date of informed consent	Date/time of first administration of study drug
On-treatment	BI pmlb, BI pmlb (l+r), BI pmlb (l+r), BI thigh respectively	Date/time of administration of study drug	Date/time of administration of Study drug + 113 * 24 h (i.e., REP of 112 days (16 weeks) + 1 day)
			or 0:00 AM on day after subject's trial completion or discontinuation date
Follow-up 	F/U BI pmlb, F/U BI pmlb (l+r), F/U BI pmlb (l+r), F/U BI thigh respectively	Date/time of administration of study drug + 113 * 24 h (i.e., REP of 112 days (16 weeks) + 1 day)	whatever comes first 0:00 AM on day after subject's trial completion or discontinuation date

 If the trial completion or discontinuation date is earlier than 113 days after date of administration of study drug, the follow-up phase does not exist for the respective subject.

CTR Section 15.3.1, Appendix 16.1.13.1.8.2 and Appendix 16.1.13.1.8.3 AE displays will present results for the on-treatment phase only. Appendix 16.1.13.1.8.1 will present results for the screening, on-treatment and follow-up phase.

In CTR Section 15.3.1 AE tables (but not in Appendix 16.1.13.1.8.2 and Appendix 16.1.13.1.8.3 AE tables), the following totals will be provided in addition:

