**7.8.5 Local tolerability**

Local tolerability (absence or presence of "swelling", "induration", "heat", "redness", "pain", or "other findings") will be summarized with counts and percentages overall (i.e. over all on-treatment time points, cf. [Section 6.1](#)) as well as by time point.

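### Do the last-value lab shift table and the on-treatment AE tables hide safety findings near peak exposure or late in follow-up?

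*SAP*

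**What the plan says.** **Laboratory data.** SAP 7.8.2 plans descriptive statistics at each time point and for the change from baseline. It then states: "Frequency tables of changes between baseline and last value on treatment with respect to the reference range will be presented". It leaves clinical significance to the investigator: "Standard or project-specific rules for flagging clinically significant values will not be applied in this study". Findings judged clinically relevant become AEs and are analysed as such. Protocol 7.3.3 adds: "Values outside the reference range as well as values defined as clinically relevant will be highlighted in the listings".

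**Analysis phases.** SAP Table 6.1: 2 applies the same phases to AEs, laboratory data, local tolerability and vital signs. On-treatment runs from dosing to 113 x 24 h, or to the end of the subject's participation if that comes first.

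**Adverse events.** Protocol 6.2.2: "AEs and concomitant therapy will be assessed continuously from screening until the end of trial examination". SAP 6.1 says of CTR Section 15.3.1 and two of the appendices: "AE displays will present results for the on-treatment phase only". Of the third it says: "Appendix 16.1.13.1.8.1 will present results for the screening, on-treatment and follow-up phase". That appendix carries a total over all study phases, screening included. SAP 7.8.1 counts subjects, not events, and gives separate tables for SAEs, AESIs and other significant AEs.

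**Local tolerability.** SAP 7.8.5: findings "will be summarized with counts and percentages overall (i.e. over all on-treatment time points", and also by time point.

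**The concern.** The shift table compares baseline with a single late value. A subject whose neutrophils, say, fall below range on Day 8 or 15 and recover by Day 92 is tabulated as having no shift. The protocol's benefit-risk section lists "Monitoring of ECG, vital signs, and extensive safety laboratory testing" among its safety measures, and safety after two periumbilical injections is a stated objective. Yet the tests nearest peak exposure do not enter the shift table. Local tolerability gets a count across all on-treatment time points; laboratory data do not.

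For AEs, the main tables stop before the Day 120, 148 and 176 visits. Because counts are by subject, on-treatment and follow-up columns cannot be added, so no described table gives, by dose group, the number of subjects with any AE from dosing to end of trial. At stake is how easily a reader sees a transient laboratory effect or a late AE. Data collection and the PK analysis are not in question.

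**Working it through.** **1. The window (reproduces SAP Table 6.1: 2).** 16 weeks x 7 = 112 days; + 1 = 113 days; x 24 = 2712 h.

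**2. Scheduled post-dose safety labs against the window** (protocol Flow Chart, the copy with the ADA column):

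| Test | Hours | Phase |
|---|---|---|
| 6 h | 6 | on-treatment |
| 48 h | 48 | on-treatment |
| Day 8 | 168 | on-treatment |
| Day 15 | 336 | on-treatment |
| Day 29 | 672 | on-treatment |
| Day 92 | 2184 | on-treatment |
| Day 176 | 4200 | follow-up |

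The 3-day visit windows do not change this: 2184 + 72 = 2256 h is still inside and 4200 - 72 = 4128 h is still outside. For a completer without later unscheduled tests, the last on-treatment value is Day 92.

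**3. Exposure at those visits.** Inputs are from protocol Table 1.2.5:3, SC groups: median tmax 6.0 and 7.0 days, half-life 25.6 and 20.6 days. Assuming log-linear decline from tmax, C/Cmax = 0.5^((d - tmax)/t1/2), with d = study day - 1:

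| Visit | Higher SC dose | Lower SC dose |
|---|---|---|
| Day 8 (d = 7) | 97% | 100% |
| Day 15 (d = 14) | 81% | 79% |
| Day 29 (d = 28) | 55% | 49% |
| Day 92 (d = 91) | 10% | 6% |

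The factual part of the concern is therefore correct.

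**4. Where an out-of-range value on Day 8, 15 or 29 still appears, even if it recovers:**

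- *Hepatic injury.* The AESI is defined by multiples of ULN, at any visit. Subjects with AESIs get their own table (SAP 7.8.1).
- *Marked laboratory abnormality.* This is the first criterion for other significant AEs, also tabulated by subject.
- *Judged clinically relevant.* It becomes an AE and is counted by subject, organ class, preferred term and maximum intensity.
- *Anything else out of range.* It contributes to the by-visit statistics and changes from baseline (SAP 7 gives minimum, median and maximum) and is highlighted in the listings. Four low values on Day 8 in a group of 12 would be four highlighted entries and would affect the Day 8 minimum.
- *Conduct.* Under protocol 3.1, laboratory tests are in the minimum data set reviewed at least 10 days after the last dosing in Dose Group 2, before Dose Groups 3 and 4 start. That decision does not wait for the report's shift table.

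What no described table counts by subject is a transient excursion that is neither clinically relevant, nor marked, nor an AESI.

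**5. What a lowest- or highest-value table would show by chance.** Assume 2.5% of values out of range on each side and independent visits.

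- One direction, seven tests: 1 - 0.975^7 = 16.2% of subjects, or 0.162 x 12 = 1.9 per group.
- Either direction, seven tests: 1 - 0.95^7 = 30.2%.
- On-treatment tests only (six): 1 - 0.975^6 = 14.1% and 1 - 0.95^6 = 26.5%.
- Simulated with within-subject correlation 0.7 (seven tests): 8.9% in one direction (1.1 of 12) and 17.8% in either.
- A single visit, as in the planned table: 2.5% in one direction, or 0.3 of 12.
- Four or more of 12 in one cell (seven tests): probability 1.8% (correlation 0.7) to 11.6% (independent).

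Protocol Table 5.2.3: 1 has about 34 repeated quantitative parameters (Quick and INR counted once). If both directions applied to each, 34 x 2 x 4 groups = 272 cells, of which 272 x 0.018 = 5 to 272 x 0.116 = 32 would show four or more of 12 with no drug effect. Parameters with only one meaningful direction lower this.

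**6. AEs.** Observation after the cut-off is 175 - 113 = 62 days, and 62/175 = 35%. The share of AUC after the cut-off is C(113) x t1/2 / ln 2, divided by AUC0-inf:

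- higher dose: 1.84 x 25.6 / 0.693 = 68, and 68/1600 = 4.3%;
- lower dose: 0.345 x 20.6 / 0.693 = 10.3, and 10.3/574 = 1.8%.

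Subjects with AEs from dosing to end = appendix total - subjects whose only AE was in screening. If 6 of 12 had an on-treatment AE and 3 of 12 a follow-up AE, those two columns alone allow 6 to 9. With no screening AEs, the total gives the number exactly; with one screening subject, it is off by at most one.

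**The case for a change.** The best case for a change is that AE counting depends on investigator judgement, and the SAP declines standard flagging rules. By-visit minima and maxima show that an extreme value occurred, but not how many subjects shifted or from what baseline, and listings must be counted by hand. The added tables would use data already collected, need no amendment, and fit protocol 7.3.3, which allows further analysis intervals.

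Part of this stands. Minor transient excursions are not counted by subject in any table the SAP describes, and a lowest- or highest-value table beside the planned one would be a legitimate choice. It would not be a clear gain: with 12 per group and no placebo arm, the chance rates in step 5 make its cells hard to interpret. The local tolerability comparison carries limited weight, because presence of redness or swelling is not measured against a reference range that healthy values cross by chance.

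The AE half is weaker. The phases follow the protocol's 16-week residual effect period, and later events are tabulated as follow-up. Without a placebo group, late AEs would be mostly background. The SAP does not say whether the appendix total is given per dose group. If it is not, the AE listings, sorted by treatment, give the number for 12 subjects per group.

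**Conclusion.** No change follows. The plan compares baseline with the last on-treatment value, a presentation choice whose limits are covered by other planned displays. For a completer the shift table uses one of seven post-dose tests, at about 6-10% of Cmax. The only findings left without a subject count are transient excursions judged neither relevant nor marked, and these remain in the by-visit statistics and highlighted listings. The AE request would repackage counts that the follow-up appendix already gives, apart from subjects with screening AEs only; about 2-4% of AUC falls after the cut-off.

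This rests on several assumptions. The exposure figures assume log-linear decline. The protocol's suggestion of target-mediated disposition limits that projection, and the redacted doses do not show which SC row applies to Dose Groups 1, 2 and 4. The chance rates assume 2.5% out of range per side. Early discontinuers may have a different last value. The sponsor's laboratory and AE reporting standards, which the SAP cites, are not in the documents and may add displays. None of these alters the conclusion: no stated rule gives a wrong result, and safety can be judged from the planned output.
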